7.2.2 Follicular lymphoma and Mantle Cell Lymphoma

FDG-PET imaging will be required during study screening. Contrast-enhanced computed tomography (CT) of the chest, abdomen, and pelvis will be performed at each tumor assessment. FDG-PET should be performed to confirm metabolic CR in patients with stable PR on 2 consecutive CT staging exams or in patients with a CR

based on CT staging and baseline FDG-avid disease to determine metabolic CR. For measurement of response, 2014 criteria as described in “Recommendations for Initial Evaluation, Staging, and Response Assessment of Hodgkin and Non-Hodgkin Lymphoma: The Lugano Classification” will be used (see Appendix 11.10) [20]. A Deauville score should be assigned when restaging PET is performed. CT imaging of the neck will be performed as indicated for standard of care.

All CT scans should be performed with IV contrast unless contraindicated, and abdominal and pelvis scans should be performed with oral contrast.

7.2.3 Marginal Zone Lymphoma and Cases of Chronic Lymphocytic Leukemia / Small Lymphocytic Lymphoma and Waldenstrom Macroglobulinemia / Lymphoplasmacytic Lymphoma in which Nodal Disease is Known or Suspected

CT of the chest, abdomen, and pelvis will be performed at each tumor assessment. For measurement of response, 2014 criteria as described in “Recommendations for Initial Evaluation, Staging, and Response Assessment of Hodgkin and Non-Hodgkin Lymphoma: The Lugano Classification” will be used (see Appendix 11.10) [20]. CT imaging of the neck will be performed as indicated for standard of care.

All CT scans should be performed with IV contrast unless contraindicated, and abdominal and pelvis scans should be performed with oral contrast.

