Overview of Study Design: Eligible patients will be entered onto the study and receive oral ixazomib weekly. A window period of six 4-week cycles of ixazomib monotherapy will be given upfront. On completion of the window period, four weekly doses of intravenous rituximab infusions will be added as ixazomib is continued. Treatment with ixazomib will continue on 4-week cycles until unacceptable drug toxicity, disease progression, or other reason as described below. The ORR of ixazomib monotherapy during the window period will be calculated before the addition of rituximab. The null hypothesis for ixazomib monotherapy in the upfront setting is an ORR < 40% and the alternative hypothesis is that the ORR exceeds 60%. A total of 36 patients will be treated.
Study Population: The study population will include patients with a diagnosis confirmed histopathologically or by flow cytometry of indolent B-NHL, including the subtypes CLL/SLL, FL, MCL, MZL, and WM/LPL. Patients will not have received standard systemic therapy for their B-NHL previously, except in cases of the MALT subtype of MZL treated with antibiotics. At the time of enrollment, patients will have measurable disease and a clinical indication for treatment.
Duration of Study: Anticipated enrollment period is 1-2 years, with total study time of approximately 5 years.

STUDY OVERVIEW DIAGRAM

SCHEDULE OF EVENTS

Study Calendar: One treatment cycle = 28 days

Required Procedures	Screening ⁶	Treatment Phase	End of Treatment ¹²
History and Physical			
Medical history	x		
Physical exam	x	X ⁹	x
ECOG performance status	x	X ⁹	x
Clinical disease assessment	x	X ⁹	x
Adverse event assessment	x	X ⁹	x
Labs and Imaging			
CBC and differential	X	X ¹⁰	X
Comprehensive metabolic panel	X	X ¹⁰	X
LDH	X	X ¹⁰	X
Beta 2 Microglobulin	X		
SPEP and immunofixation ¹	X	X ¹¹	X
CT chest, abdomen, pelvis ²	X	X ¹¹	X
FDG-PET (base of skull to proximal femur) ³	X	X	
Bone marrow studies ⁴	X	X	
Pregnancy test	X ⁷		
Pathologic studies	X ⁸	X ⁸	
Tumor Assessment ⁵	X	X ¹¹	X

¹ In cases of WM/LPL.

² In cases of radiographically measurable disease (see section 7.2). Note this may not be present for cases of CLL and WM. Imaging of the neck is suggested for clinically evident or previously described cervical disease.

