7.1.1 Determination of Sample Size

The sample size was determined to gain a preliminary assessment of the efficacy of ixazomib in untreated subtypes of B-NHL. The ORR for effective single-agent therapy in patients with indolent B-NHL is approximately 40 to 70% [19]. In this single-stage phase II study, the null hypothesis that the true response rate is $\leq 40\%$ will be tested against the alternative hypothesis that the true response rate is $\geq 60\%$ with a type I error rate of 8% and a power of 85%. An ORR of at least 19 out of 36 will be required to conclude promising efficacy.

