7.2.4 Chronic Lymphocytic Leukemia / Small Lymphocytic Lymphoma

CBC and differential will be performed on peripheral blood samples at each tumor assessment. For measurement of response, 2008 criteria as described in “Guidelines for the diagnosis and treatment of chronic lymphocytic leukemia: a report from the International Workshop on Chronic Lymphocytic Leukemia updating the National Cancer Institute-Working Group 1996 guidelines” will be used (see Appendix 11.11) [21].

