7.2.5 Waldenstrom Macroglobulinemia / Lymphoplasmacytic Lymphoma

Serum protein electrophoresis (SPEP) and immunofixation will be performed on peripheral blood samples at each tumor assessment. For measurement of response, 2011 criteria as described in “Report from the Sixth International Workshop on Waldenström's Macroglobulinemia” will be used (see Appendix 11.12) [22].

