11.8 The Lugano Response Classification: For FL, MZL, and MCL [20]

Response and Site	PET-CT–Based Response	CT-Based Response
Complete	Complete metabolic response	Complete radiologic response (all of the following)
	Score 1, 2, or 3 ⁺ with or without a residual mass on 5PS [†]	Target nodes/nodal masses must regress to ≤ 1.5 cm in LDi
Lymph nodes and extralymphatic sites	It is recognized that in Waldeyer's ring or extranodal sites with high physiologic uptake or with activation within spleen or marrow (eg, with chemotherapy or myeloid colony-stimulating factors), uptake may be greater than normal mediastinum and/or liver. In this circumstance, complete metabolic response may be inferred if uptake at sites of initial involvement is no greater than surrounding normal tissue even if the tissue has high physiologic uptake	No extralymphatic sites of disease
Nonmeasured lesion	Not applicable	Absent
Organ enlargement	Not applicable	Regress to normal
New lesions	None	None
Bone marrow	No evidence of FDG-avid disease in marrow	Normal by morphology; if indeterminate, IHC negative
Partial	Partial metabolic response	Partial remission (all of the following)
Lymph nodes and extralymphatic sites	Score 4 or 5 [†] with reduced uptake compared with baseline and residual mass(es) of any size	$\geq 50\%$ decrease in SPD of up to 6 target measurable nodes and extranodal sites
	At interim, these findings suggest responding disease	When a lesion is too small to measure on CT, assign 5 mm \times 5 mm as the default value
	At end of treatment, these findings indicate residual disease	When no longer visible, 0 \times 0 mm
		For a node > 5 mm \times 5 mm, but smaller than normal, use actual measurement for calculation
Nonmeasured lesions	Not applicable	Absent/normal, regressed, but no increase
Organ enlargement	Not applicable	Spleen must have regressed by $> 50\%$ in length beyond normal
New lesions	None	None
Bone marrow	Residual uptake higher than uptake in normal marrow but reduced compared with baseline (diffuse uptake compatible with reactive changes from chemotherapy)	Not applicable

Response and Site	PET-CT–Based Response	CT-Based Response
	allowed). If there are persistent focal changes in the marrow in the context of a nodal response, consideration should be given to further evaluation with MRI or biopsy or an interval scan	
No response or stable disease	No metabolic response	Stable disease

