- * A score of 3 in many patients indicates a good prognosis with standard treatment, especially if at the time of an interim scan. However, in trials involving PET where de-escalation is investigated, it may be preferable to consider a score of 3 as inadequate response (to avoid undertreatment). Measured dominant lesions: Up to six of the largest dominant nodes, nodal masses, and extranodal lesions selected to be clearly measurable in two diameters. Nodes should preferably be from disparate regions of the body and should include, where applicable, mediastinal and retroperitoneal areas. Non-nodal lesions include those in solid organs (eg, liver, spleen, kidneys, lungs), GI involvement, cutaneous lesions, or those noted on palpation. Nonmeasured lesions: Any disease not selected as measured, dominant disease and truly assessable disease should be considered not measured. These sites include any nodes, nodal masses, and extranodal sites not selected as dominant or measurable or that do not meet the requirements for measurability but are still considered abnormal, as well as truly assessable disease, which is any site of suspected disease that would be difficult to follow quantitatively with measurement, including pleural effusions, ascites, bone lesions, leptomeningeal disease, abdominal masses, and other lesions that cannot be confirmed and followed by imaging. In Waldeyer's ring or in extranodal sites (eg, GI tract, liver, bone marrow), FDG uptake may be greater than in the mediastinum with complete metabolic response, but should be no higher than surrounding normal physiologic uptake (eg, with marrow activation as a result of chemotherapy or myeloid growth factors).
- † PET 5PS: 1, no uptake above background; 2, uptake ≤ mediastinum; 3, uptake > mediastinum but ≤ liver; 4, uptake moderately > liver; 5, uptake markedly higher than liver and/or new lesions; X, new areas of uptake unlikely to be related to lymphoma.

11.9 Response and Progression Criteria for CLL [21, 24].

Parameter	CR (all criteria must be met) ¹	PR (all criteria from Group A and one from Group B must be met)	PD (at least one criteria from Group A of one from Group B must be met) ²	Stable disease (all criteria must be met)
Group A				
Lymphadenopathy ³	None > 1.5 cm	Decrease ≥50% ⁴	Increase ≥50% or any new LN > 1.5 cm ⁵	Change of -49% to +49%

Blood lymphocytes	< 4,000/ μ L	Decrease \geq 50% from baseline	Increase \geq 50% over baseline (\geq 5,000/ μ L) ⁶	Change of -49% to +49%

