⁶ In the absence of other objective evidence of PD, lymphocytosis alone should not be considered an indicator of PD. Patients with lymphocytosis and no other evidence of PD should continue therapy until they develop at least one other criteria suggesting progressive disease other than lymphocytosis.

⁷ If abnormal before therapy

⁸ An increase in the previously noted enlargement of the liver or spleen by 50% or more or the de novo appearance of hepatomegaly or splenomegaly.

⁹ Hypocellular marrow defines CRi (complete response with incomplete marrow recovery).

¹⁰ Without the need for exogenous growth factors or transfusions.

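### Nodal CLL/SLL and WM/LPL are each given two response criteria with no rule on which governs, and the CLL table, read literally, bars PR for a patient who enters on lymphocytes alone

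*Combined protocol and SAP*

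**What the plan says.** Section 7.2.3 covers MZL and also "Cases of Chronic Lymphocytic Leukemia / Small Lymphocytic Lymphoma and Waldenstrom Macroglobulinemia / Lymphoplasmacytic Lymphoma in which Nodal Disease is Known or Suspected". For all of these it requires CT at each tumor assessment and names the 2014 Lugano classification for measuring response.

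Section 7.2.4 then deals with CLL/SLL as a whole: "For measurement of response, 2008 criteria as described in" the CLL workshop guideline. Section 7.2.5 does the same for WM/LPL: "For measurement of response, 2011 criteria as described in" the sixth Waldenström workshop report. Neither section excludes patients with nodal disease.

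The title of Appendix 11.8 reads "The Lugano Response Classification: For FL, MZL, and MCL". In Appendix 11.9 the partial-response column is headed "PR (all criteria from Group A and one from Group B must be met". Footnote 7 to that table, "If abnormal before therapy", is marked in the PR column on the hepatomegaly cell only.

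Section 7.3 makes investigator-assessed ORR the primary endpoint. It counts CR and PR for CLL/SLL, FL, MZL and MCL. For WM/LPL it also counts very good partial response and minor response. Section 7.1.1 sets the decision rule at 19 or more responders of 36, "with a type I error rate of 8% and a power of 85"%.

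**The concern.** A patient with nodal CLL/SLL or nodal WM/LPL falls under two sections, each of which prescribes a different response system without qualification. The systems measure different things: Lugano by CT looks at nodes, organs and new lesions, 11.9 adds blood lymphocytes and counts, and 11.10 is driven by serum IgM. Where they disagree, the plan leaves the choice to the investigator. The study is open-label and single-arm, and its primary endpoint rests on that same investigator's assessment.

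The CLL table adds a second problem. PR requires every Group A item, and most of these ask for a fall of at least 50%. Section 5.1 lets a patient enter on a single measurable-disease criterion. A patient whose nodes are normal at entry cannot show a 50% fall in them.

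At stake are the pooled ORR that feeds the 19-of-36 rule, the ORR of each disease cohort, and the progression dates behind PFS and DOR.

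**Working it through.** **1. Which criterion applies to whom**

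| Patient | 7.2.3 | 7.2.4 / 7.2.5 | Appendix title |
|---|---|---|---|
| Nodal CLL/SLL | Lugano | 2008 CLL criteria | 11.8 leaves out CLL/SLL; 11.9 is for CLL |
| Nodal WM/LPL | Lugano | 2011 WM criteria | 11.8 leaves out WM/LPL; 11.10 is for WM/LPL |

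The cross-references do not settle it. Section 7.2.3 sends the reader to 11.10 for Lugano, but 11.10 is the WM/LPL list. Section 7.2.4 points to 11.11, which is CTCAE. Section 7.2.5 points to 11.12, which does not exist. Each pointer is two too high.

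**2. Nodal CLL, ORR.** Take a 60% fall in the sum of products of diameters (SPD) and a 20% fall in lymphocytes, with the other Lugano CT conditions for PR met (spleen, nonmeasured lesions, no new lesions).
- By 11.8: 60% is at least 50%, so PR.
- By 11.9: the nodal item is met, but the lymphocyte item needs at least 50% and 20% fails. Not PR.

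**3. Nodal WM, ORR.** Take a 30% IgM fall and a 20% SPD fall. By 11.10 this is a minor response, and by Lugano CT it is stable disease. Section 7.3 counts minor response for WM/LPL with no nodal exception, and that category exists only in 11.10. For ORR the text therefore points to 11.10.

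**4. WM, PFS and DOR.** Section 7.3 does not reach these. An IgM rise of at least 25%, confirmed by a second measurement, is progression by 11.10. Lugano has no IgM criterion.

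**5. Group A items for PR in 11.9**

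| Item | Condition for PR | Baseline exemption printed |
|---|---|---|
| Nodes | fall of at least 50% | none |
| Lymphocytes | fall of at least 50% | none |
| Liver | fall of at least 50% | footnote 7 |
| Spleen | fall of at least 50% | none on its row; ambiguous (see the objection) |
| Marrow | none | not needed |

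A CLL patient who enters on lymphocytes alone, without enlarged nodes, cannot meet the nodal item. That patient has no Lugano route either, because 7.2.3 covers only nodal cases.

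**6. Design figures.** Inputs from 7.1.1: n = 36, cut-off 19, response rates 0.40 and 0.60. With X binomial:
- P(X ≥ 19 | 0.40) = 0.0826, against a stated 8%.
- P(X ≥ 19 | 0.60) = 0.8540, against a stated 85%.

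Both reproduce to the nearest whole percent.

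**7. Weight of one patient.** 1/36 = 2.8 percentage points. One patient can change the conclusion only if the count is 18 (moved up) or 19 (moved down):

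| True ORR | P(X = 18) | P(X = 19) | Sum |
|---|---|---|---|
| 40% | 0.063 | 0.040 | 0.103 |
| 50% | 0.132 | 0.125 | 0.257 |
| 60% | 0.063 | 0.090 | 0.153 |

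The 40% row follows from the tails: P(X ≥ 18) − P(X ≥ 20) = 0.1460 − 0.0426 = 0.103. The 60% row is 0.9174 − 0.7640 = 0.153. In the limiting case where exactly one patient is always counted up, type I error would be 0.146 rather than 0.083. Where exactly one is always lost, power would be 0.764 rather than 0.854.

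**The case against.** The strongest reply is that disease-specific criteria were plainly intended. Section 7.2.1 speaks of assessment by subtype, the title of 11.8 names three histologies, 7.3 uses WM-only categories, and both 11.9 and 11.10 already take nodes by CT. On that view, 7.2.3 carries one stray sentence. As evidence of intent this stands, and for WM/LPL it largely settles ORR. It does not settle nodal CLL/SLL, because CR and PR exist under both systems and 7.2.3 speaks of measuring response, not only of imaging.

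The Group A wording also has a fair defense. Footnote 8 is marked on the liver row, yet its text covers liver and spleen, so footnote 7 may reach the spleen too. The 2008 guideline that 7.2.4 invokes may also make the exemption clear, but it is not reproduced. This is why the spleen row is called ambiguous here. It does not help the nodal row.

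Three stronger readings are tempting and not supported:
- A reader might infer that any normal Group A baseline rules out PR. It does not: the liver is exempted and marrow carries no PR condition.
- A reader might infer that an SLL patient with a normal lymphocyte count can never reach PR. As the plan stands, one with measurable nodes can do so by Lugano through 7.2.3.
- A reader might infer that CLL/SLL ORR will be biased downward. That assumes investigators would demand a 50% fall in a finding that was absent, which the documents do not show.

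**Conclusion.** The point holds. The plan gives nodal CLL/SLL and nodal WM/LPL two response systems and no rule of precedence. For nodal CLL/SLL this leaves the primary endpoint undetermined. For WM/LPL it leaves the progression date undetermined. The literal bar to PR in 11.9 is established for lymphocyte-only CLL without enlarged nodes and is uncertain for the spleen.

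The size cannot be estimated, because the documents give no number of nodal CLL/SLL or WM/LPL patients and no rate of disagreement between the systems. Each reclassified patient shifts pooled ORR by 2.8 points, and shifts a single cohort's ORR by more. A reader might take the 10%, 26% and 15% as the chance that this defect changes the conclusion. They are only an upper bound on a one-patient flip: such a flip also needs a patient on whom the criteria disagree, in the direction that matters. The 50% value is neither of the design's hypotheses and is shown for range.

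**What to change.** For the ORR, DOR and PFS analyses, name one governing criterion per histology, in line with the title of 11.8 and with 7.3: 11.8 for FL, MZL and MCL; 11.9 for all CLL/SLL; 11.10 for all WM/LPL. In 7.2.3, keep CT as the source of the nodal component and remove the Lugano response sentence as it applies to CLL/SLL and WM/LPL. Correct the appendix pointers in 7.2 to 11.8, 11.9 and 11.10.

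In 11.9, state that the PR items for nodes, lymphocytes, liver and spleen apply only if abnormal at baseline. Make this change together with the first. Otherwise SLL patients with normal counts lose the Lugano route and still fail the lymphocyte item as printed.

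No new assessments are needed, because CT, CBC and SPEP are already scheduled. The document is dated December 2023, so responses may already be recorded. Any that are affected should be reclassified from existing data, at small cost. N = 36 and the 19-responder rule are unchanged.

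Section 4.3 ties progression before rituximab to stopping treatment. Where the choice of progression criterion bears on that, the sponsor must reconcile the passages; this point concerns the analyses only.

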7.2.4 Chronic Lymphocytic Leukemia / Small Lymphocytic Lymphoma

CBC and differential will be performed on peripheral blood samples at each tumor assessment. For measurement of response, 2008 criteria as described in “Guidelines for the diagnosis and treatment of chronic lymphocytic leukemia: a report from the International Workshop on Chronic Lymphocytic Leukemia updating the National Cancer Institute-Working Group 1996 guidelines” will be used (see Appendix 11.11) [21].

7.2.5 Waldenstrom Macroglobulinemia / Lymphoplasmacytic Lymphoma

Serum protein electrophoresis (SPEP) and immunofixation will be performed on peripheral blood samples at each tumor assessment. For measurement of response, 2011 criteria as described in “Report from the Sixth International Workshop on Waldenström's Macroglobulinemia” will be used (see Appendix 11.12) [22].

7.2.6 Bone marrow aspirate and biopsy

A bone marrow aspirate and biopsy will be obtained before the first dose of study drug, and for confirmation of CR when indicated. Bone marrow aspirate and biopsy requirements may be waived by the Sponsor-Investigator or sub-Investigator. These samples will be evaluated locally.

7.3 Primary Efficacy Endpoint

Response assessments will be performed by the investigators. All measurable disease should be documented at screening and re-assessed at each subsequent tumor evaluation.

All patients treated with ixazomib will be considered evaluable for assessment of

response, with the following exceptions: 1) patients who missed $\geq 50\%$ of scheduled doses of ixazomib prior to first scheduled treatment-phase tumor evaluation, unless due to related AE or progressive disease, will not be considered evaluable for assessment of response; 2) patients who did not undergo scheduled treatment-phase tumor evaluation, unless due to progressive disease, will not be considered evaluable for assessment of response.

The primary efficacy endpoint is the overall response rate (CR + PR for CLL/SLL, FL, MZL, and MCL; CR + Very Good PR + PR + Minor Response for WM/LPL) as assessed by the investigators. ORR will be calculated for all treated patients for each disease cohort. The corresponding 95% two-sided confidence interval will be derived.

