4.2 Number of Patients

A total of 36 patients will be enrolled. Enrollment will be defined as the day the subject is registered and assigned a study-specific subject number. Estimated distribution of the study population by gender, race, and ethnicity:

Table 4-1 Estimated distribution of patients by ethnicity, race, and gender

Ethnic / Racial Category	Females	Males
American Indian/Alaska Native		
Asian	1	1
Native Hawaiian or Other Pacific Islander		
Black or African American		1
White	16	16
More than one race		
Unknown or not reported	1	
Total of all subjects	18	18

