7.1.3 Populations for Analysis

Efficacy will be evaluated at pre-specified restaging evaluations. Subjects must complete the first scheduled tumor evaluation or have progressive disease or intolerance of ixazomib prior to the first scheduled tumor evaluation to be evaluable for efficacy.

Safety and tolerability will be evaluated in all subjects that received at least 1 dose of ixazomib.

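### Sections 7.1.3 and 7.3 give three conflicting denominators for the primary ORR, and the 19-of-36 rule has no cut-off for any other number

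*Combined protocol and SAP*

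**What the plan says.** Three statements define the denominator.

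- **Section 7.1.3.** A patient is evaluable after completing the first scheduled tumor evaluation. The alternative is to "have progressive disease or intolerance of ixazomib prior to the first scheduled tumor evaluation to be evaluable for efficacy". Early intolerance is therefore kept.
- **Section 7.3, two exceptions.** Exception 1 removes patients who missed at least half of their doses before the first evaluation, unless a related adverse event or progression was the cause. Exception 2 reads: "patients who did not undergo scheduled treatment-phase tumor evaluation, unless due to progressive disease, will not be considered evaluable for assessment of response". Its only excuse is progression.
- **Section 7.3, last paragraph.** "ORR will be calculated for all treated patients for each disease cohort".

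The decision rule in 7.1.1 is: "An ORR of at least 19 out of 36 will be required to conclude promising efficacy". It does not say which population the 36 is. Section 4.2 says: "A total of 36 patients will be enrolled. Enrollment will be defined as the day the subject is registered", whereas the Protocol Summary gives 36 as the number treated. I found no replacement rule, no allowance for non-evaluable patients, and no cut-off for a number other than 36. The rule is for the pooled 36, while 7.3 describes ORR by disease cohort.

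**The concern.** Consider a patient who stops ixazomib for toxicity at week 5 and has no treatment-phase scan. The first evaluation is due at week 8 (Schedule of Events, footnote 11). That patient is in under 7.1.3, out under exception 2 of 7.3, and in again under the last paragraph of 7.3. The two exceptions also disagree with each other: a related adverse event excuses missed doses but not a missed evaluation.

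Such a case is foreseeable. Footnote 12 asks for an end-of-treatment tumor assessment only when none was done within 60 days. If a recent screening scan satisfies that, an early stopper may properly have no further scan.

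A patient who leaves unevaluated has no documented response, so excluding that patient can only raise the observed ORR. The trial is single-arm and open-label, and the investigators assess response. With three readings available, the choice could be made after the responses are known, and with fewer than 36 analysed the success rule is undefined.

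**Working it through.** **Inputs.** From 7.1.1: null rate 40%, alternative 60%, error 8%, power 85%, at least 19 responders of 36. The direction of the hypotheses makes the test one-sided. The number of excluded patients is not in the documents; I assume 1 to 4.

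**Step 1: the plan's own figures.** Let X be the number of responders, binomial with n = 36.

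- P(X ≥ 19 | 36, 0.40) = 0.0826
- P(X ≥ 19 | 36, 0.60) = 0.8540

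These match 8% and 85%. Neighbouring cut-offs do not: 18/36 gives 14.6% and 91.7%; 20/36 gives 4.3% and 76.4%.

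**Step 2: non-responders excluded, cut-off rescaled.** With k treated non-responders dropped, n = 36 − k. If the true all-treated rate is p, the rate among those left is 36p/(36 − k). The cut-off r is the smallest count with r/n ≥ 19/36 = 52.8%.

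| Dropped k | Rule r/n | Evaluable rate when p = 40% | P(success), p = 40% | P(success), p = 60% |
|---|---|---|---|---|
| 0 | 19/36 | 40.0% | 8.3% | 85.4% |
| 1 | 19/35 | 41.1% | 8.0% | 85.9% |
| 2 | 18/34 | 42.4% | 14.1% | 92.6% |
| 3 | 18/33 | 43.6% | 13.8% | 93.1% |
| 4 | 17/32 | 45.0% | 22.7% | 97.0% |

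The steps come from rounding: the required count falls from 19 to 18 at k = 2 and to 17 at k = 4. As a cross-check, requiring 18 responders among all 36 treated gives 14.6%, close to the 14.1% at k = 2.

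**Step 3: non-responders excluded, count of 19 kept.** Dropping non-responders leaves the number of responders unchanged. With k = 4 the evaluable rates are 0.40 × 36/32 = 45.0% and 0.60 × 36/32 = 67.5%. Then P(X ≥ 19 | 32, 0.450) = 7.3% and P(X ≥ 19 | 32, 0.675) = 87.8%. Error does not inflate and power is not lost.

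**Step 4: all treated counted.** With 36 treated and unevaluated patients counted as non-responders, Step 1 applies unchanged.

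**The case against.** The strongest reply is that the plan already names the right population. The sentence in 7.3 that says how ORR is calculated uses all treated patients, and the Protocol Summary gives 36 treated. On that reading 19/36 performs as stated. This is correct as far as it goes. But the same section has just declared some treated patients not evaluable for response, and nothing says that they are then counted as non-responders. The sentence can equally be read as all treated patients who remain evaluable.

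A reader might infer four stronger things, which the documents do not support.

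- **That the 8% and 85% are wrong.** They are right at 36. Any departure needs actual exclusions and a rescaled cut-off; one exclusion leaves the error at 8.0%.
- **That 7.1.3 also discards early treatment failures.** It expressly keeps early progression and early intolerance. It loses only those who leave early for other reasons, such as withdrawal.
- **That needing 19 of 32 cuts power to 60.4%.** That figure puts the 60% rate on the 32 evaluable patients. If the four dropped are non-responders, the all-treated rate is then 0.60 × 32/36 = 53.3%, which is not the design alternative. At an all-treated 60%, power is 87.8%.
- **That excluded patients would be replaced until 36 are evaluable, inflating the error further.** No replacement rule exists, and the stated total is 36.

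**Conclusion.** The conflict stands and should be resolved before the primary ORR is interpreted. It concerns which patients are counted; the sample-size arithmetic is sound. Applying the 7.3 exclusions as written would remove foreseeable treatment failures and bias ORR upward.

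The effect on the decision is conditional. It is nil if all 36 treated patients are counted with unevaluated patients as non-responders, and there is no inflation if 19 is kept as a count. If non-responders are excluded and the cut-off becomes a proportion, the false-positive rate is about 14% with two or three exclusions and about 23% with four, against 8.3% by design. These figures assume that everyone dropped is a non-responder and that one to four patients are dropped. The rescaled cut-off is also my assumption, since the plan gives none.

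**What to change.** 1. In 7.3, define the primary denominator as all patients who received at least one dose of ixazomib. Count any patient without a documented response in the monotherapy window as a non-responder, whatever the reason.
2. In 7.1.1, state that 19/36 applies to that set, pooled across disease cohorts; cohort ORRs are then descriptive.
3. List exact-binomial cut-offs in case the number treated is not 36, and state the criterion used to choose them. Examples: 18/34 (error 8.7%, power 84.5%), 19/35 (6.2%, 80.7%), 20/37 (5.9%, 81.8%), 20/38 (7.8%, 86.2%). If the error may not exceed the 8.3% of the current rule, 34 treated would need 19 (4.4%, 74.9%).
4. Move the two 7.3 exceptions to a response-evaluable sensitivity analysis, and align 7.1.3 with it.

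The cost is wording only, with no added patients or procedures, though the reported ORR may be slightly lower. The document is dated December 2023 and 4.4 refers to a November 2022 modification, so window-period results may already be known. If they are, the change must be disclosed as late, and ORR is best shown under all three denominators.
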